8.4 Guidelines for Management of Treatment Emergent Hepatotoxicity

Event	Dose Modification Algorithms
(A). ALT of $\leq 3.0 \times \text{ULN}$	Continue pazopanib at current dose with full panel LFTs ⁰ monitored as per protocol.
(B). ALT $>3.0 \times \text{ULN}$ to $\leq 8.0 \times \text{ULN}$ without bilirubin elevation (defined as total bilirubin ⁰ $<2.0 \times \text{ULN}$ or direct bilirubin $\leq 35\%$) and without hypersensitivity symptoms (e.g., fever, rash)	
Liver Event Monitoring Criteria:
 
(1) Continue pazopanib at current dose levels.
 
(2) Monitor subject closely for clinical signs and symptoms; perform full panel LFTs^a weekly or more frequently if clinically indicated until ALT/AST is reduced to Grade 1.

(C). ALT $>8.0 \times \text{ULN}$ without bilirubin elevation (defined as total bilirubin ^b $<2.0 \times \text{ULN}$ or direct bilirubin $\leq 35\%$) and without hypersensitivity symptoms (e.g., fever, rash)	
1st occurrence – Liver Event Interruption Criteria⁰:
 
(1) Interrupt pazopanib until toxicity resolves to \leqGrade 1 or baseline. Report the event to Novartis as an SAE within 24 hours of learning of its occurrence and complete the eCRF liver event forms. Make every reasonable attempt to have subjects return to the clinic within 24 to 72 hours for repeat liver chemistries and liver event follow up assessments.
 
(2) Liver imaging and other laboratory investigations should be considered as clinically appropriate.
 
(3) Monitor subject closely for clinical signs and symptoms; perform full panel LFTs^a weekly or more frequently if clinically indicated until ALT/AST is reduced to Grade 1.
 
(4) If the subject is benefiting from the study treatment, contact Novartis Study Physician for possible re-challenge. Re-treatment may be considered if ALL following criteria are met:
 
 - ALT/AST reduced to Grade 1 - Total bilirubin $<1.5 \times \text{ULN}$ or direct bilirubin $\leq 35\%$ - No hypersensitivity signs or symptoms - Subject is benefiting from therapy. 
Recurrence – Liver Event Stopping Criteria⁰:
 
Discontinue pazopanib permanently and monitor subject closely for clinical signs and symptoms; perform full panel LFTs^a weekly or more frequently if clinically indicated until ALT/AST is reduced to Grade 1. At the time of the recurrence, complete the eCRF liver event forms.

Event	Dose Modification Algorithms

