- 15.26 Due to the similarity in nature of this agent to other VEGF inhibitors (bevacizumab, VEGF-trap, etc.) monitor for signs of bleeding, thrombosis and PE. Instruct patient to report any calf tenderness, shortness of breath, chest pain or bleeding immediately.
- 15.27 Cytopenias are common. Monitor CBC w/diff and instruct patient to report any unusual bruising or bleeding and/or signs of infection to study team.
- 15.28 Monitor LFT's. Patients who have AST/ALT levels > 3x ULN and concurrent bilirubin >2X ULN should permanently discontinue pazopanib. Patients with AST/ALT levels as above and mild hyperbilirubinemia (with suspected or known Gilbert's syndrome) should be monitored weekly while continuing pazopanib.
- 15.29 Cardiac side effects (CHF, MI, chest pain, etc). while rare can be serious and life threatening. Instruct patient to report any cardiac symptoms to study team immediately.
- 15.29a RPLS, CVA, and TIA are uncommon, but are life threatening. Instruct patient to report any neurological symptoms to the study team immediately.

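### For ALT above 8x ULN with mild hyperbilirubinemia and Gilbert's syndrome, 15.28 continues pazopanib while 8.4 row C interrupts it and then stops it, and neither section is said to control

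*Combined protocol and SAP*

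**What the plan says.** Section 15.28 has two dosing sentences on liver tests. The first reads: "Patients who have AST/ALT levels > 3x ULN and concurrent bilirubin >2X ULN should permanently discontinue pazopanib". The second concerns "Patients with AST/ALT levels as above and mild hyperbilirubinemia" where Gilbert's syndrome is known or suspected, and says they "should be monitored weekly while continuing pazopanib".

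Section 8.4 sets out hepatotoxicity management in rows keyed to ALT:

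- **Row B** (ALT above 3x and up to 8x ULN, no bilirubin elevation, no hypersensitivity symptoms): "Continue pazopanib at current dose levels", with liver panels at least weekly.
- **Row C** (ALT above 8x ULN, same bilirubin and hypersensitivity conditions). At first occurrence: "Interrupt pazopanib until toxicity resolves to" Grade 1 or lower, or baseline, with a report to the company as an SAE. Re-challenge is possible after recovery, subject to listed conditions and contact with the company's study physician. On recurrence: "Discontinue pazopanib permanently and monitor subject closely for clinical signs and symptoms".

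Both rows treat bilirubin as not elevated if total bilirubin is below 2.0x ULN **or** the direct fraction is 35% or less.

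**The concern.** The only transaminase level to which the second sentence of 15.28 can point back is the first sentence's 3x ULN, which is a floor without a ceiling. Read as written, the Gilbert's sentence therefore reaches patients whom row C takes off drug.

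At stake is whether a patient with a marked ALT rise keeps taking pazopanib, and whether one with a second such rise is stopped for good. The per-patient rules carry more weight because the accrual-suspension rule in 16.42 leaves out abnormal liver function tests, so these events do not count toward pausing the study. Section 1.5 also says the protocol is meant to give clear management guidance for such events.

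**Working it through.** The plan gives no figure to reproduce. The check is whether one patient can satisfy both texts, and whether any other text settles the matter.

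**Step 1: place the Gilbert's patient in 8.4.** Mild hyperbilirubinemia with total bilirubin below 2x ULN, or mainly indirect bilirubin, meets the definition of no bilirubin elevation used in rows B and C. Row D needs total bilirubin of at least 2.0x ULN with more than 35% direct, or hypersensitivity symptoms, so it does not apply.

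**Step 2: compare the instructions.**

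| ALT | 15.28, second sentence | 8.4 | Result |
|---|---|---|---|
| Above 3x, up to 8x ULN | Continue, weekly monitoring | Row B: continue, at least weekly panels | Agree |
| Above 8x ULN, first time | Continue, weekly monitoring | Row C: interrupt | Conflict |
| Above 8x ULN, recurrence | Continue, weekly monitoring | Row C: permanent stop | Conflict |

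**Step 3: worked case.** Known Gilbert's, ALT 10x ULN, total bilirubin 1.6x ULN, direct 20%, no hypersensitivity symptoms. ALT 10x exceeds both 3x and 8x. Bilirubin 1.6x is below 2.0x, and 20% is below 35%. Both texts apply and their actions differ.

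**Step 4: look for a text that resolves it.**

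- 8.4 has no row or note for Gilbert's syndrome.
- Its isolated-hyperbilirubinemia row requires ALT below 3x ULN.
- 15.15(c) repeats the stop for AST/ALT above 3x with bilirubin above 2x ULN, but has no Gilbert's sentence.
- 15.28 does not refer to 8.4, and no section states precedence.

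**Step 5: limits of the conflict.** Row C is triggered by ALT, so AST alone above 8x ULN does not create it. Such patients can be enrolled: 3.16 admits total bilirubin below 1.5x ULN provided ALT and AST are not also above ULN.

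**Step 6: size.** The documents give neither the share of patients above 8x ULN nor the frequency of Gilbert's syndrome. Table 79 (Appendix VIII, RCC study, pazopanib arm) describes only a broader group: Grade 3 plus Grade 4 ALT increase is 10% + 2% = 12%, and any-grade bilirubin increase is 36%. For the 39 planned patients:

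- if the two are independent (assumption): 0.12 x 0.36 = 0.043, and 0.043 x 39 = 1.7 patients;
- with no assumption on their association, the overlap lies between 0 (because 0.12 + 0.36 is below 1) and 0.12, and 0.12 x 39 = 4.7, so 0 to 4.7 patients.

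This group is not restricted to ALT above 8x ULN, to mild bilirubin elevation, to Gilbert's syndrome, or to both abnormalities occurring together.

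**The case against.** The best defence is that 15.28 is a short nursing item under Drug Information, while dose changes have their own section and 8.4 is devoted to hepatotoxicity. On that view 15.28 abbreviates row B and omits the 8x limit, and staff would defer to 8.4. Its neighbour 15.23 refers staff to the study guidelines and to physician orders. Moreover, 8.4 does accommodate Gilbert's-type bilirubin in substance, because its 35% direct-fraction criterion keeps mainly indirect elevations out of row D.

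Much of this is fair. Row B is probably what the sentence had in mind, and it is speculative to say that staff would actually dose through an event. But the sentence is a dosing instruction, nothing limits it to row B's range, and no precedence is written. Row C's re-challenge provision does not help either: it follows interruption and recovery, so it is not the same as continuing.

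Three stronger inferences are tempting but not supported:

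- **That SAE counts would depend on which section was read.** 15.28 waives no reporting, and the table in 10.51 separately requires ALT above 8x ULN without bilirubin elevation to be reported within 24 hours on the SAE tool.
- **That 15.28 contradicts itself because *mild* might exceed 2x ULN.** The term is undefined, but the preceding sentence deals with bilirubin above 2x ULN and the second is set against it. The natural reading of *mild* is not above 2x.
- **That about two patients would be affected.** The 1.7 figure describes a different, broader group.

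**Conclusion.** The point holds in a narrow form. For ALT above 8x ULN with mild hyperbilirubinemia, suspected or known Gilbert's syndrome and no hypersensitivity symptoms, the protocol gives opposite instructions: continue under 15.28, but interrupt and, on recurrence, permanently stop under 8.4 row C. Between 3x and 8x ULN the two agree.

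The conclusion rests on reading the back-reference in 15.28 as AST/ALT above 3x ULN, the only level stated there, and *mild* as within row C's bilirubin limits.

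Few patients would be affected. If ALT above 8x ULN falls within Grade 3 to 4 (an assumption, since the protocol does not reproduce the grade limits), the conflict group is a part of the Table 79 overlap, by a fraction the documents do not give. The 12-month survival endpoint, the sample size and the analyses do not depend on it. It deserves correction because it concerns patient safety and is easily removed. Nothing here implies a view on which instruction is clinically right.

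**What to change.** Reconcile 15.28 with 8.4 so that one rule applies to these patients. One way is for 15.28 to refer to the section that controls and to state the ALT range and bilirubin limit that its Gilbert's sentence covers; another is to add a Gilbert's row or note to 8.4. The clinical team decides the content.

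The same edit can settle a separate mismatch between these sections. The first sentence of 15.28 stops pazopanib at AST/ALT above 3x with bilirubin above 2x ULN whatever the direct fraction, whereas row D also looks at whether more than 35% is direct. There 15.28 is the stricter text; here it is the looser one, so the edit must address both sentences.

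The cost is about one sentence in an amendment, with no added tests, patients or analyses.

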16.0 Statistical Considerations and Methodology

- 16.1 Overview: This protocol will assess the efficacy of pazopanib in patients with non-clear cell metastatic renal cancer using a one-stage phase II study design.
- 16.11 Primary Endpoint: The primary endpoint of this trial is the 12-month overall survival rate. A “12-month overall survivor” will be considered synonymous with “success”, unless otherwise specified. A patient is considered to be a 12-month survivor if the patient lives 12 months from registration (note, all deaths prior to 12 months, regardless of cause, will be considered a failure). All patients meeting the eligibility criteria who have signed a consent form and have begun treatment will be evaluable for the primary endpoint. All eligible patients will be followed until death or a minimum of 2 years.
- 16.2 Statistical Design:
- 16.21 Decision Rule: The largest success proportion where the proposed treatment regimen would be considered ineffective in this population is 55%, and the smallest success proportion that would warrant subsequent studies with the proposed regimen in this patient population is 75%. The one-stage design based on properties of the binomial distribution uses 39 patients to test the null hypothesis that the true success proportion in a given patient population is at most 55%.
- 16.22 Sample Size: There will be 35 evaluable patients accrued onto this study unless undue toxicity is encountered. We anticipate accruing an additional 4 patients to account for ineligibility, cancellation, major treatment violation, or other reasons.
- 16.23 Accrual Time and Study Duration: The anticipated accrual rate is approximately 1-2 patients per month, based on the incidence of tumor type and the potential to accrue at Mayo Clinic sites (Mayo Clinic Rochester, Mayo Clinic Florida and Mayo Clinic Arizona). Therefore, the accrual period for this phase II study is expected to be 24 months. The final analysis can begin approximately 36 months after the trial begins, i.e. as soon as the last patient has been observed for 12 months.
- 16.24 Power and Significance Level: The null 12-month overall survival rate of 55% is based on the Kaplan-Meier estimate of 12-month survival from the Mayo Clinic Nephrectomy database (Leibovich, Lohse et al.). Assuming that the number of successes is binomially distributed and the significance level is ≤ 0.10 , we are required to accrue evaluable 35 patients to achieve an 80% power under the alternative hypothesis of a 75% success proportion.
- 16.3 Analysis Plan: The analysis for this trial will commence at the time all patients have become evaluable for the primary endpoint. Such a decision will be made by the Statistician and Study Chair, in accord with standard operating procedures, availability of data for secondary endpoints, and the level of data maturity.

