1.4 Mayo Clinic Nephrectomy database experience with non clear cell renal cell cancer

At the Mayo Clinic (Rochester), (Department of Urology) an active kidney tumor registry has been maintained since 1970. The Nephrectomy Registry is currently complete with clinical follow up through 2007 and provides a rich source of clinical outcomes based on various histological subtypes. Between 1970 and 2007, 3714 nephrectomies for RCC were performed that had a specific RCC histo-path subtype with a breakdown as follows:

3051 clear cell RCC

499 papillary RCC

156 chromophobe RCC

8 collecting duct RCC

(Sarcomatoid differentiation can arise in all of these subtypes and is not considered a separate subtype according to the AJCC classification)

Among the 663 nephrectomies for non-clear cell RCC, 26 were M1 at nephrectomy and 48 subsequently developed metastases sometime following nephrectomy. For the 74 cases with distant metastases either at nephrectomy or following nephrectomy, the overall survival rates at 1, 3, and 5 years following distant metastases were 55.2%, 24.9%, and 16.3%, respectively (Leibovich, Lohse et al.). Non-clear cell metastatic RCC survival

reported from another large kidney cancer database from Memorial Sloan Kettering, published by Motzer et al (Motzer, Bacik et al. 2002) also provides insight into the poor prognosis of these histological subtypes. Of the 64 patients followed between 1985 and 2001, the median survival of metastatic non clear cell RCC was found to be 9.4 months, with survival longer for patients with chromophobe tumors than with collecting duct and papillary cancers. Patients in this review had received cytokine and or hormonal treatments with negligible responses highlighting an unmet need for the treatment in this group of patients.

Mayo Clinic (Rochester) annually averages 4-6 metastatic non-clear cell RCCs that undergo nephrectomy with a similar incidence at Mayo Clinic, Florida and Arizona. In addition in the Medical Oncology division at Rochester between 3 and 7 metastatic non-clear cell RCCs are treated annually.

Since the role of active treatment agents in metastatic RCC of non-clear-cell histologies remains to be established and the efficacy of pazopanib in delaying disease progression in metastatic clear cell RCC is unknown in non clear cell histological sub types, the current prospective phase II trial is designed to evaluate the efficacy of pazopanib in advanced stage non clear RCC patients.

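### The plan contradicts itself on whether 35 or 39 patients are tested and prints no cut-off; its 55% null comes from survival after metastasis in nephrectomised patients, and its fit to registrants is not supported.

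*Combined protocol and SAP*

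**What the plan says.** **Who is tested.** Section 16.21 says the one-stage design "uses 39 patients to test the null hypothesis that the true success proportion in a given patient population is at most 55" percent. Section 16.22 says "There will be 35 evaluable patients accrued onto this study unless undue toxicity is encountered", with 4 more expected to cover ineligibility, cancellation, major violation and similar losses. Section 16.24 also bases the power on 35 evaluable patients: significance level at most 0.10, and 80% power if the true proportion is 75%. Section 16.313 says that patients beyond the target number play no part in decisions but do enter the final estimates. No section gives the number of successes needed.

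**Where the null comes from.** Section 16.24 says "The null 12-month overall survival rate of 55% is based on the Kaplan-Meier estimate of 12-month survival from the Mayo Clinic Nephrectomy database". Section 1.4, citing the same source, reports that "the overall survival rates at 1, 3, and 5 years following distant metastases were 55.2%, 24.9%, and 16.3%, respectively". Those figures describe 74 non-clear-cell cases, all nephrectomised, of whom "26 were M1 at nephrectomy and 48 subsequently developed metastases sometime following nephrectomy". The registry period is long: "Between 1970 and 2007, 3714 nephrectomies for RCC were performed".

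**What the trial counts.** Section 16.11 says "A patient is considered to be a 12-month survivor if the patient lives 12 months from registration". Section 3.13 allows one prior treatment for metastatic disease, and section 3 requires neither nephrectomy nor recent metastasis. Section 16.311 scores loss to follow-up before 12 months as failure. Section 16.312 plans a success proportion with confidence intervals.

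**The concern.** In a single-arm trial the fixed null and the cut-off are the whole comparison. Two things are unsettled here.

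First, if 39 evaluable patients are available, the plan supports two readings. Either the first 35 decide and 4 are surplus under 16.313, or all 39 decide. With no printed cut-off, the choice could be made after the outcomes are known.

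Second, the benchmark clock starts at distant metastasis and the trial clock starts at registration. A patient who registers some months after metastasis has already survived part of the period that the benchmark covers. Selection differs too: the registry cases all had a nephrectomy, while the trial admits patients with one prior treatment, ECOG status up to 2, and histologies outside the registry's breakdown (oncocytic, sarcomatoid, translocation, medullary). No section argues that 55% carries over. If the no-effect rate in registrants is above 55%, the stated alpha is too low.

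**Working it through.** **Inputs.** Null 0.55, alternative 0.75, alpha at most 0.10, power 80% (16.21, 16.24). n = 35 (16.22, 16.24) or 39 (16.21). Registry survival 55.2%, 24.9% and 16.3% at 1, 3 and 5 years in 74 cases (1.4).

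**1. Reproduce the plan's figure.** For a cut-off of c successes among n, alpha = P(X ≥ c | n, 0.55) and power = P(X ≥ c | n, 0.75), exact binomial:

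| n | c | alpha | power | meets both limits |
|---|---|---|---|---|
| 35 | 23 | 0.134 | 0.924 | no |
| 35 | 24 | 0.073 | 0.858 | yes |
| 35 | 25 | 0.035 | 0.758 | no |
| 39 | 24 | 0.256 | 0.980 | no |
| 39 | 25 | 0.163 | 0.956 | no |
| 39 | 26 | 0.095 | 0.914 | yes |
| 39 | 27 | 0.050 | 0.846 | yes |
| 39 | 28 | 0.024 | 0.747 | no |

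The stated 35 is therefore adequate, and it implies one cut-off, 24. At 39 two cut-offs qualify. The 24 is derived here, not printed, so the sponsor must confirm it.

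**2. How much error in the null the rule tolerates.** Solving P(X ≥ c | n, p) = 0.10 for p gives 0.565 for 24/35, 0.552 for 26/39 and 0.579 for 27/39. For 24/35, the chance of a positive trial with no drug effect is:

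| no-effect rate | 0.45 | 0.50 | 0.55 | 0.58 | 0.61 | 0.65 |
|---|---|---|---|---|---|---|
| alpha | 0.004 | 0.021 | 0.073 | 0.136 | 0.230 | 0.402 |

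**3. What the documents say about the no-effect rate.**
- *Sampling error.* Treating 55.2% as a simple proportion of 74 (an assumption; censoring would widen the interval): 0.552 ± 1.96 × √(0.552 × 0.448/74) = 0.552 ± 1.96 × 0.0578, or about 0.44 to 0.67.
- *Upward.* Average yearly survival between years 1 and 3 after metastasis is √(0.249/0.552) = 0.67. Patients registering some time after metastasis would move the rate toward that value. Selection on performance status, laboratory values, and CNS and cardiac disease could also raise it.
- *Downward.* Prior treatment, aggressive histologies and scoring loss as failure could lower it. For a second series, section 1.4 says "the median survival of metastatic non clear cell RCC was found to be 9.4 months". If survival is exponential (an assumption), that is 0.5^(12/9.4) = 0.41 at 12 months. The 13.4-month median in section 1.2 gives 0.54, and the 63-week median in section 1.3 gives 0.56.

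The documents do not give time from metastasis to registration, so these pulls cannot be netted.

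**The case against.** Historical nulls in single-arm phase II trials are always approximate. This one is disclosed with its source, and the patients come from the same institution that keeps the registry. The confidence interval in 16.312 lets a reader set the result against any other benchmark. Converted as above, the other series give 0.56, 0.54 and 0.41, and at 24/35 the corresponding alphas are 0.097, 0.055 and 0.001, all within 0.10. On 35 versus 39, section 16.22 explains the extra 4 as an attrition allowance.

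Most of this stands. It rules out calling 55% wrong. It does not remove the points that the plan never says 55% is conditional on registrants resembling the registry, and that the confidence interval reflects only the trial's own sampling error. The attrition explanation makes 35 the likelier intention, but 16.21 still says the test uses 39.

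A reader might go further in three ways that the documents do not support:
- *That alpha is really near 0.50.* That needs every registrant to behave like a registry patient already a year past metastasis. Nothing in the plan says so.
- *That power is lost if the true null is below 55%.* Sections 16.21 and 16.24 define the target as an absolute 75%, and power there is 0.858 at 24/35 whatever the no-effect rate. A loss appears only if the target is recast as a hazard ratio, which the plan never states.
- *That a registry-matched analysis is required.* It would rest on few registry patients at later times, with no matching on performance status, histology or era. It is optional.

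**Conclusion.** The contradiction over the test set is an error as written: 39 in 16.21, 35 in 16.22 and 16.24, and no cut-off. It matters because 24 successes carries alpha 0.073 among 35 patients and 0.256 among 39.

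The applicability of the 55% is a gap in support, not a demonstrated bias. The time origin and the selection differ from the trial's, the direction of any error is unknown, and the margin is small: about 1.5 percentage points at 24/35 (0.565 − 0.55) before alpha passes 0.10, and about 0.2 points at 26/39. At no-effect rates of 58% and 61%, alpha at 24/35 would be 0.136 and 0.230. These results assume independent patients and read the 0.10 as the chance of a positive trial at 55%, since the plan does not state sidedness. The sample-size arithmetic itself is sound.

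**What to change.** In 16.21 to 16.24:
1. State that the test uses the first 35 evaluable patients, and change the 39 in 16.21 to match.
2. Print the rule: 24 or more successes among 35, with alpha 0.073 and power 0.858.
3. State that alpha at most 0.10 holds only if the no-effect rate in registrants is at most 55%.
4. Add a short table of alpha for no-effect rates on both sides of 55%, such as the one in the working.

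On the On-Study form, record the date of first distant metastasis if it is not already there (the form's content is not shown). In 16.31, plan to describe the 12-month result by prior treatment and by time since metastasis, as description only, with no bearing on the primary conclusion.

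The cost is a few sentences, one table and at most one date per patient. The sample size and the primary test do not change. The downside is that the stated error control is shown to be conditional, so a just-positive result may have to be reported more cautiously.
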